1. PROTOCOL SUMMARY

1.1. Synopsis

Not applicable.

1.2. Schema

1.3. Schedule of Activities (SoA)

The table provides an overview of the protocol visits and procedures. Refer to [STUDY ASSESSMENTS AND PROCEDURES](#) section of the protocol for detailed information on each procedure and assessment required for compliance with the protocol. The investigator may schedule visits (unplanned visits) in addition to those listed in the SoA table, in order to conduct evaluations or assessments required to protect the well-being of the participant.

Visit Identifier/Day [for list of abbreviations refer to Section 10.9]	Screen ≤-28 to -2	Day -1	Day 1													Day 2		Day 3 ^a	Day 4 ^a	ET	Follow-Up
			0	0.5	1	2	4	6	7	8	10	12	14	16	24	36	48	72	Day 30±2		
Hours Post Dose		--	0	0.5	1	2	4	6	7	8	10	12	14	16	24	36	48	72	--	--	
Informed consent & demography	X																				
Outpatient visit	X																	X ^a	X		
Inpatient stay at Clinical Research Unit		X	→	→	→	→	→	→	→	→	→	→	→	→	→	→	X ^a	X ^a			
Eligibility assessment	X	X																			
Medical history	X	X																			
Physical exam (height & body weight at Screen, only) ^b	X	X															X ^c	X ^c	X		
Breath alcohol test	X	X																			
Alcohol/tobacco & contraception use	X	X																X ^{c,d}	X	X ^e	
(Update) prior/concomitant treatments	X	X																X ^{c,d}	X	X	
Single, supine 12-lead ECG	X		X														X ^c	X ^c	X		
Single, seated vital sign assessment (BP and pulse rate)	X		X														X ^c	X ^c	X		
Serious and non-serious adverse event monitoring	X	X	→	→	→	→	→	→	→	→	→	→	→	→	→	→	X ^c	X ^c	X	X	
Standard meals ^f		X	X			X		X		X		X		X		X	X	X ^c			
Investigational product administration			X ^g																		
Blood for clinical laboratory tests after ≥4-hour fast	X		X														X ^c	X ^c	X		
Blood FSH (females only), HIV, HBsAg, HCVAb/RNA	X																				
Blood for pregnancy test (females only)	X		X														X ^c	X ^c	X		
CCI																					
Blood for pharmacokinetic sampling for PF-06865571			X	X	X	X	X	X		X	X	X		X	X	X	X	X ^c	X		
Urine drug test		X																			
Urinalysis (and microscopy, if needed)	X		X														X ^c	X ^c	X		
Urine pregnancy test (WOCBP, only)			X																		

- Participants discharged post completion of procedures (Cohort 1, *only*); in Cohorts 2-4, discharge (with subsequent outpatient visit) permitted *or* stay can continue to Day 4.
- Full physical (PE) exam at Screen; at all other time points, limited PE for findings during previous PE or new/open AEs *only*, at Investigator discretion.
- On Day 3**, procedures limited to Cohort 1, *only*; **on Day 4**, procedures limited to Cohorts 2-4, *only*.
- In Cohorts 2-4 *only*, procedures to be completed *only if* participant is discharged on Day 3 and returns for outpatient visit on Day 4.
- Confirmation of appropriate contraception use *only*.
- Meals/snacks to be served at clock times matching approximately 0H, 4H, 7H, 10H, and 14H (optional) relative to dosing on Day 1 (while inpatient).
- Dosing to occur with standard morning meal provided approximately 30 minutes prior to 0H, and completed approximately 10 minutes prior to dosing.

2. INTRODUCTION

Diacylglycerol acyltransferases (DGATs) catalyze the terminal step in triglyceride (TG) synthesis; specifically, the esterification of a fatty acid (FA) with diacylglycerol (DAG) resulting in the formation of TG.¹ In mammals, 2 structurally unrelated DGAT enzymes (DGAT1 and DGAT2) have been characterized. DGAT1 is highly expressed in the intestine and plays a central role in fat absorption.² DGAT2 is highly expressed in liver and adipose.³ PF-06865571 is an oral, small molecule DGAT2 inhibitor that is postulated to decrease hepatic TG synthesis and hepatic lipid burden in non-alcoholic fatty liver disease (NAFLD) and non-alcoholic steatohepatitis (NASH). Based on observations in nonclinical studies conducted with PF-06865571, it is hypothesized that DGAT2 inhibition will impact both physiological drivers contributing to NASH via direct inhibition of liver triglyceride synthesis, as well as adaptive responses leading to reduction in hepatic de novo lipogenesis (DNL). Following 2 weeks of dosing in participants with NAFLD, PF-06865571 has been shown to reduce liver fat in a dose-responsive manner.

2.1. Study Rationale

The primary purpose of this non-randomized, open-label study is to characterize the effect of varying degrees of hepatic impairment on the plasma pharmacokinetics (PK) of PF-06865571 following administration of a single, oral, 100 mg dose of PF-06865571. NAFLD/NASH is associated with varying degrees of hepatic impairment. Recognizing that the target population of PF-06865571 is patients with NAFLD/NASH and CCI [REDACTED] the current study is proposed to evaluate whether there is any clinically meaningful effect of hepatic impairment on the plasma PK of PF-06865571.

2.2. Background

CCI [REDACTED]

[REDACTED]

[REDACTED]

[REDACTED]

[REDACTED]

CCI

CCI

2.2.3. Clinical Overview

As of the issuance of this protocol, 6 clinical studies have completed dosing with PF-06865571 (C2541001, C2541002, C2541003, C2541005, C2541006, and C3711002). Refer to the PF-06865571 investigator's brochure for more details on Studies C2541001, C2541002, C2541003, and C3711002. CCI

A total of 168 participants have been randomized across the 6 clinical studies and exposed to at least 1 dose of the investigational product (PF-06865571, and/or matching placebo) across the clinical studies conducted with PF-06865571.

CCI

2.3. Benefit/Risk Assessment

PF-06865571 is not expected to provide any clinical benefit to participants in this study. This study is designed primarily to generate pharmacokinetic data to inform further clinical development in the target population of patients with NASH. The data from this study will contribute to dosing recommendations of PF-06865571 for the treatment of NASH acknowledging that the target patient population includes those with varying degrees of hepatic impairment.

PF-06865571 has been administered as single doses in healthy subjects, as repeated doses in healthy adults and patients with NAFLD, and as modified-release formulation, as well as in combination with metformin. It has been observed to be well-tolerated with an acceptable safety profile at single oral doses as high as 1500 mg and repeated, oral doses of up to 1800 mg/day (as 600 mg every 8 hours [Q8H]) for a duration of up to 14 days with the maximum tolerated dose not identified. As of the issuance of this protocol, no specific human risks have been identified. The clinical impact of any *potential* risks in this study will be minimized through the proposed close, inpatient monitoring during the dosing period along with the selection of a dose (100 mg) which is 15-fold lower than the highest single dose administered thus far.

Based on the safety profile of PF-06865571 observed in clinical studies to date, the risk to the participants in this study is deemed to be minimal. More detailed information about the known and expected benefits and risks and reasonably expected adverse events of PF-06865571 may be found in the investigator’s brochure for PF-06865571, which is the single reference safety document (SRSD) for this study.

3. OBJECTIVES AND ENDPOINTS

Objectives	Endpoints
Primary:	Primary:

 To compare the PK of PF-06865571 following administration of a single oral dose in adult participants with varying degrees of hepatic impairment relative to age- and body weight-matched participants without hepatic impairment. 	
 PF-06865571 PK parameters derived from plasma: C_{max}, AUC_{last}, and AUC_{inf}.
Secondary:	Secondary:

 To evaluate the safety and tolerability of a single oral dose of PF-06865571 when administered to adult participants with varying degrees of hepatic impairment relative to age- and body weight-matched participants without hepatic impairment. 	
 Assessment of treatment-emergent adverse events, clinical laboratory tests, vital signs, and 12-lead ECGs.
CCI [REDACTED]	[REDACTED]
[REDACTED]	[REDACTED]

4. STUDY DESIGN

4.1. Overall Design

This is a Phase 1, non-randomized, open-label, single-dose, parallel-cohort, multicenter study to compare the pharmacokinetics of PF-06865571 in adult participants with varying degrees of hepatic impairment relative to participants without hepatic impairment after a single, oral 100 mg dose administered in the fed state. A total of approximately 24 participants with varying degrees of hepatic function will be dosed in the study as shown in [Table 1](#).

Table 1. Hepatic Function Categories Based on Child Pugh Score

Cohort	Description	Child-Pugh Score	Number of Subjects
1	Without hepatic impairment	Not Applicable	6a
2	Mild hepatic impairment	Class A (5 to 6 points)	6
3	Moderate hepatic impairment	Class B (7 to 9 points)	6
4	Severe hepatic impairment	Class C (10 to 15 points)	6b

[figure not shown]
- a. Additional participants may be dosed to a maximum of 8 participants to ensure mean age ± 5 years and mean body weight ± 10 kg of this cohort is aligned with the pooled average assessed when $\geq 75\%$ of participants are dosed across the other 3 cohorts.
- b. If recruitment across the sites selected proves to be prohibitive, study will dose only 4 participants in this cohort.

Categorization of participants into Cohort 2-4, inclusive, will be done based on Child-Pugh scores determined, as described in [Appendix 8](#), at the Screening visit. Participants will be dosed in a staged manner such that those with moderate and severe hepatic impairment (Cohorts 3 and 4) will be evaluated first. Dosing in participants with mild hepatic impairment (Cohort 2) will initiate when approximately 50% of the total participants in Cohorts 3 and 4 have been dosed. Participants without hepatic impairment (Cohort 1) will be recruited near the end of the study to match the average demographics (at a minimum, age and weight; and gender as much as practically possible) across the pooled Cohorts 2 through 4. **Approval from the sponsor must be obtained before proceeding with recruitment for participants in Cohort 1 or Cohort 2.**

Participants who prematurely discontinue for non-safety related reasons may be replaced, at the discretion of the principal investigator (PI) and sponsor study team.

The overall study design is summarized in [Figure 1](#). For individual participants, the total duration of participation from the Screening visit to the follow-up visit will range from 5 weeks (minimum) to 9 weeks (maximum).

Figure 1. Study Design

4.2. Scientific Rationale for Study Design

This study involves participants with varying degrees of hepatic impairment and participants without hepatic impairment, matched for age as well as body weight (and gender as much as practically possible). A single dose of PF-06865571 is proposed since single dose plasma PK is generally predictive of exposure upon repeated dosing, especially given that the observed relatively short terminal half-life ($t_{1/2}$) of PF-06865571 resulted in minimal accumulation upon repeated dosing of both Q8H and Q12H frequency.

CCI [REDACTED]

[REDACTED] serial PK samples will be collected over 48 hours in participants without hepatic impairment (Cohort 1). CCI [REDACTED]

[REDACTED] serial PK samples will be collected over 72 hours postdose to adequately characterize the elimination phase of the plasma concentration-time profile in the cohorts with varying degrees of hepatic function (Cohorts 2-4).

Malnutrition is prevalent in patients with chronic liver disease, and regular meals are an important aspect for their health. CCI [REDACTED]

[REDACTED] PF-06865571 administration is planned to occur with the morning standard meal in this study to ensure consistency with the intended dosing scheme in the target patient population.

In general, participants with normal hepatic function (Cohort 1) will abstain from all concomitant treatments, except for the treatment of adverse events. Participants with impaired hepatic function (Cohorts 2, 3, and 4) are permitted to be on stable doses of background medications for the management of their concomitant medical condition(s) with some exclusions. Specifically, strong CYP3A inhibitors, strong and moderate CYP3A inducers, and time-dependent inhibitors of CYP3A are excluded from this study in participants with impaired hepatic function ^{CCI}

^{CCI} In addition, moderate CYP3A inhibitors will not be co-administered with PF-06865571 on Day 1 of this study. Similarly, BCRP substrates (eg, rosuvastatin) and sensitive CYP2C9 substrates will not be administered on Day 1 ^{CCI}

^{CCI} P-gp inhibitors (eg, digoxin) are excluded from this study. ^{CCI}

^{CCI} Participants taking metformin must not take a morning dose of metformin on Day 1 of this study.

The Child-Pugh classification (CPC; refer to [Appendix 8](#)) will be used to define the 3 cohorts of participants with varying degrees of hepatic impairment. This study will include participants with mild (Child-Pugh Class A, Cohort 2), moderate (Child-Pugh Class B, Cohort 3), and severe (Child-Pugh Class C, Cohort 4) hepatic impairment as well as demographic-matched control participants without hepatic impairment (Cohort 1). All 3 categories of hepatic impairment will be assessed, as these represent the likely population in later phase studies for the proposed indication of treatment of NASH. All participants will be required to provide their own consent to participate in this study, hence participants with clinically-active Grade 3 or Grade 4 encephalopathy will be excluded. However, participants who have a previous history of Grade 3 or Grade 4 encephalopathy but are currently receiving an intervention [for example: lactulose or lactitol, alone or in combination with rifaximin, and/or neomycin] to control their encephalopathy-related signs and symptoms are eligible provided the on-treatment encephalopathy grading at the Screening visit is Grade 2 or lower thereby permitting them to provide their own informed consent. Acknowledging the medical state of the population enrolled, certain eligibility criteria for participants with hepatic impairment are distinctly different, including assessment of Hepatitis B and Hepatitis C, with no specific exclusion of those who have these conditions planned for participants classified in Cohorts 2, 3, or 4.

^{CCI} Participants will be excluded if there is concomitant clinical evidence of renal impairment, defined as estimated glomerular filtration rate (eGFR) ≤ 60 mL/min. This is to enable a more clear assessment of the effect of hepatic impairment on PF-06865571 disposition.

CCI

[REDACTED] all female participants of childbearing potential, at risk of pregnancy, are required to use highly effective methods of contraception during this study. In addition, male participants must use barrier methods of contraception to minimize transfer of drug to their female partner(s). Refer to [Section 10.4](#) for details regarding contraception guidance.

CCI

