5. STUDY POPULATION

This study can fulfill its objectives only if appropriate participants are enrolled. The following eligibility criteria are designed to select participants for whom participation in the study is considered appropriate. All relevant medical and nonmedical conditions should be taken into consideration when deciding whether a particular participant is suitable for this protocol.

Prospective approval of protocol deviations to recruitment and enrollment criteria, also known as protocol waivers or exemptions, is not permitted.

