5.2. Exclusion Criteria

Participants are excluded from the study if any of the following criteria apply:

Medical Conditions:

1. Any condition possibly affecting drug absorption (eg, prior bariatric surgery, gastrectomy, ileal resection).

NOTE: Participants who have undergone cholecystectomy and/or appendectomy are eligible for this study as long as the surgery occurred more than 6 months prior to Screening.
2. At Screening, participants with a positive result for human immunodeficiency virus (HIV) antibodies, as assessed by sponsor-identified central laboratory, with a single repeat permitted to assess eligibility, if needed.
3. Other acute or chronic medical or psychiatric condition including recent (within the past year) or active suicidal ideation or behavior or laboratory abnormality that may increase the risk associated with study participation or investigational product administration or may interfere with the interpretation of study results and, in the judgment of the investigator, would make the participant inappropriate for entry into this study.

Prior/Concomitant Therapy:

4. Use of prior/concomitant therapies as outlined in [Section 6.5](#).

Prior/Concurrent Clinical Study Experience:

5. Previous administration with an investigational drug within **30 days** (or as determined by the local requirement) or 5 half-lives preceding the first dose of investigational product used in this study (whichever is longer).
6. Participants with known prior participation (ie, randomized and received at least 1 dose of investigational product) in a study involving PF-06865571.

Diagnostic Assessments:

7. A positive urine drug test, for illicit drugs on Day -1, as assessed by sponsor-identified central laboratory. However, **participants in Cohorts 2-4, only**, who have been medically prescribed opiates/opioids or benzodiazepines and report the use of these drugs to the investigator at the screening visit will be allowed to participate.

NOTE: repeat urine drug testing is not permitted in this study.

8. At Screening **or** Day -1, a positive breath alcohol test, as assessed using kits provided by sponsor-identified central laboratory, with a single repeat **on a separate day** permitted to assess eligibility, if needed.

Other Exclusions:

9. Male participants with partners who are currently pregnant.
10. Blood donation (excluding plasma donations) of approximately 1 pint (500 mL) or more within 60 days prior to dosing and until the follow-up contact.

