6.5.2. Participants with Impaired Hepatic Function (Cohorts 2, 3, and 4)

Participants are permitted to be on stable doses of background medications for the management of their concomitant medical condition(s). Whenever possible, attempts must be made to not alter the doses and regimens of the concomitant medications after Day 1 and until the follow-up contact.

- Participants on the following medications, at the Screening visit, are excluded from the study:
 - Potent CYP3A inhibitors (eg, boceprevir, clarithromycin, conivaptan, grapefruit juice, indinavir, itraconazole, ketoconazole, lopinavir/ritonavir, mibefradil, nefazodone, nelfinavir, posaconazole, ritonavir, saquinavir, telaprevir, telithromycin, voriconazole);
 - Time-dependent CYP3A inhibitors (eg, diltiazem, erythromycin, and verapamil);

- Potent and moderate CYP3A inducers (eg, avasimibe, bosentan, carbamazepine, efavirenz, etravirine, modafinil, nafcillin, phenytoin, rifampin, St. John's wort);
- P-gp substrates (eg, digoxin);
- (Medical grade) marijuana, regardless of medical indication.
- Participants ***must not take the following medications on Day 1*** of this study:
 - Moderate CYP3A inhibitors (eg, amprenavir, aprepitant, atazanavir, ciprofloxacin, crizotinib, darunavir/ritonavir, fluconazole, fosamprenavir, imatinib);
 - Sensitive CYP2C9 substrates and substrates with a narrow therapeutic range (eg, fluvastatin, diclofenac, celecoxib, toseamide, warfarin, phenytoin).
- Participants ***must not take a morning dose of the following medications on Day 1*** of this study:
 - OCT2/MATE1 substrates (eg, metformin);
 - BCRP substrates (eg, rosuvastatin, atorvastatin, simvastatin, fluvastatin).

Herbal supplements must be discontinued ***at least 28 days*** prior to Day 1 and until the follow-up contact.

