5.6.1. Deviations Assessed Prior to Dosing

At Screening, the investigator will assess participants against the inclusion and exclusion criteria as set out in Sections 5.1 and 5.2 of the protocol.

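### Does naming P-gp inhibitors in Section 4.2 but P-gp substrates in Section 6.5.2 leave eligibility for Cohorts 2 to 4 undefined?

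*Protocol*

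**What the plan says.** Section 4.2 of the protocol, the scientific rationale for the design, summarises the co-medication restrictions for participants with hepatic impairment. On P-glycoprotein it says "P-gp inhibitors (eg, digoxin) are excluded from this study". On two other classes it says "BCRP substrates (eg, rosuvastatin) and sensitive CYP2C9 substrates will not be administered on Day 1", and the text straight after that is redacted. It then says "Participants taking metformin must not take a morning dose of metformin on Day 1 of this study".

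Section 6.5.2 is the list for Cohorts 2, 3 and 4 and has three tiers. The first opens "Participants on the following medications, at the Screening visit, are excluded from the study" and includes "P-gp substrates (eg, digoxin"; it has no entry for P-gp inhibitors. The second names drugs not to be taken at all on Day 1: moderate CYP3A inhibitors, and sensitive CYP2C9 or narrow-therapeutic-range substrates. The third bars only the morning dose on Day 1, for OCT2/MATE1 substrates and BCRP substrates.

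The link to eligibility is exclusion criterion 4 in Section 5.2, "Use of prior/concomitant therapies as outlined in" Section 6.5. Section 5 adds "Prospective approval of protocol deviations to recruitment and enrollment criteria, also known as protocol waivers or exemptions, is not permitted". SAP Section 5.6.1 says "At Screening, the investigator will assess participants against the inclusion and exclusion criteria as set out in Sections 5.1 and 5.2 of the protocol".

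**The concern.** Three things look wrong when Sections 4.2 and 6.5.2 are read together.

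- **P-gp class.** One section names inhibitors and the other substrates, both with digoxin as the example. Someone taking a P-gp inhibitor that Section 6.5.2 does not otherwise list seems barred by Section 4.2 but eligible under Section 6.5.2. Someone taking a P-gp substrate other than digoxin seems to be in the reverse position.
- **BCRP timing.** Section 4.2 appears to rule out BCRP substrates for the whole of Day 1. Section 6.5.2 withholds only the morning dose.
- **Double listing.** Fluvastatin and phenytoin each appear under two rules of different strictness in Section 6.5.2. So does ritonavir, if combination products are split into components.

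What would be at stake is who may enrol and what counts as a protocol deviation. The cohorts are small: 6 participants each, with Cohort 4 allowed to fall to 4. One person admitted or refused on the wrong class word would be 1/6 = 17% or 1/4 = 25% of a cohort. Because waivers are barred, the enrolment wording has to carry the decision.

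**Working it through.** No power, variance or interval figure is involved, so the check is a comparison of texts.

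**Step 1: rules visible in Section 4.2 against Section 6.5.2** (reading strong and potent as the same).

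| Section 4.2 rule | Section 6.5.2 | Result |
|---|---|---|
| Strong CYP3A inhibitors | Screening exclusion | compatible |
| Strong and moderate CYP3A inducers | Screening exclusion | compatible |
| Time-dependent CYP3A inhibitors | Screening exclusion | compatible |
| Moderate CYP3A inhibitors, Day 1 | not on Day 1 | compatible |
| Sensitive CYP2C9 substrates, Day 1 | not on Day 1 (also narrow therapeutic range) | compatible, wider |
| Metformin, morning of Day 1 | no morning dose (all OCT2/MATE1 substrates) | compatible, wider |
| P-gp inhibitors | P-gp substrates, Screening exclusion | class word differs |
| BCRP substrates, Day 1 | no morning dose on Day 1 | apparent timing difference; 4.2 redacted after Day 1 |

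That is 6 + 1 + 1 = 8 rules.

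**Step 2: which text decides eligibility.** Exclusion criterion 4 refers to Section 6.5. SAP Section 5.6.1 refers to protocol Sections 5.1 and 5.2, which contain criterion 4. Neither refers to Section 4.2. A site applying the criteria reads one P-gp rule, the one in Section 6.5.2.

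**Step 3: P-gp users under each section.**

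- Digoxin: barred by both.
- P-gp inhibitor not otherwise listed: barred by 4.2, not listed in 6.5.2.
- P-gp substrate other than digoxin: barred by 6.5.2, not mentioned in the visible text of 4.2.

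The third line is silence beside redacted text, which is not permission. The two exclusions are also logically compatible, since a plan could intend both. What is shown is that the sections do not match, not that a particular one is false.

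**Step 4: double listings in Section 6.5.2.** Example entries across the eight classes: 17 + 3 + 10 + 1 + 9 + 6 + 1 + 4 = 51. Counted as printed, two drugs repeat:

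- Fluvastatin: not on Day 1 (CYP2C9), and no morning dose on Day 1 (BCRP).
- Phenytoin: Screening exclusion (inducer), and not on Day 1 (CYP2C9).

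Splitting combination products adds a third, ritonavir: a Screening exclusion on its own and within lopinavir/ritonavir, and under the Day 1 rule within darunavir/ritonavir.

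Every line is a prohibition, so they apply together. For phenytoin, and for ritonavir on the component reading, the Screening exclusion operates first and the Day 1 line has nothing left to do. For fluvastatin, keeping to the whole-day line also meets the morning-dose line.

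**The case for a change.** The strongest reply is that an operative list is not necessarily the intended list. If Section 4.2 states the intent, criterion 4 lets in people whom the design meant to keep out, and because they meet the criteria as written no eligibility deviation would be logged. If Section 6.5.2 states the intent, the published rationale is wrong. The class words are legible in both places, so the nearby redactions cannot remove the mismatch. It could also be said that no sentence makes the stricter line prevail for a drug listed twice, and that a site might treat darunavir/ritonavir as restricted only on Day 1.

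Part of this stands. The P-gp labels do not match, and the documents do not show which class was meant. The darunavir/ritonavir entry could be read by product or by component.

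The consequences are weaker. With one list in force, eligibility and deviation status are determinate, whatever was intended. Deviation review is not confined to the Screening check: SAP Sections 5.6 and 5.6.2 provide for a full list of deviations, and for any significant one to be reviewed before database closure with a decision for each analysis population. SAP Section 5.6 separately allows participants with events that may affect their PK profile to be excluded from the PK analysis. The bar on waivers concerns approving deviations from the criteria; it does not stop the sponsor clarifying a word. The 17% and 25% shares show how much one participant weighs in a cohort, not that anyone would be misclassified.

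The BCRP point cannot be judged, because a qualifier may lie in the redacted text. A drug that belongs to two classes will naturally be an example of both.

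**Conclusion.** The concern does not call for a change to the plan. It comes down to one clerical mismatch, in the P-gp class word, between a rationale section and the list that criterion 4 makes operative. That is 1 of the 8 co-medication rules visible in Section 4.2, and the only P-gp drug named in either place is excluded by both. The BCRP difference rests on a sentence cut by redaction, and the double listings (two as printed, three by component) are cumulative rules that do not conflict.

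Nothing here touches the sample size, the one-way ANOVA, the analysis sets or the 90% confidence intervals, and no shift in the AUC or Cmax ratios is shown. The two P-gp passages must still be reconciled as a matter of wording, so that both name the same class or classes. That is an editorial task for the sponsor, and no position is taken on which is right.

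The conclusion assumes that sites enrol from the numbered criteria and Section 6.5, and that the redacted text holds no competing eligibility rule. It would need another look if the sponsor confirmed that the operative list omits a class it meant to exclude; the documents do not show that.
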